6.3.1.2.2 Guidance for corticosteroids tapering for management of immune-related AEs

Reduce prednisone dose by 2.5- to 5.0-mg decrements every 3–7 days until physiologic dose (5 to 7.5 mg of prednisone per day) is reached. Consider to complete tapering over a period of at least 4 weeks. Slower tapering of corticosteroids therapy may be recommended if the adverse event is not showing improvement. Once corticosteroid tapering is achieved at a level of 10 mg of prednisone/day (or equivalent), treatment with PDR001 can be restarted as indicated in the dose modification tables.

6.3.1.3 Dose modification requirements for adverse events suspected to be related to study treatment

The required dose modification and management of adverse events that are considered to be related to study medication and do not have specific management requirements noted elsewhere in the protocol are provided in [Table 6-11](#) and [Table 6-12](#).

Table 6-11 Mandatory dose modification requirements and recommended clinical management guidelines for hematologic adverse events suspected to study treatment

Hematologic suspected AEs (NCI-CTCAE v4.03)		
Grade	Recommended Adverse Event management guidelines	Mandatory Dose Modification requirements
Neutropenia		
Grades 1, 2	NA	Continue PDR001 treatment
Grade 3, 4	Monitoring blood test more frequently (every 7 days for grade 3, and 3-5 days for grade 4)	
1st occurrence:
 
 Interrupt PDR001 until toxicity recovers to Grade ≤2 or baseline. 
 Once recovered restart PDR001 treatment at the same dose and schedule 
2nd occurrence:
 
 Interrupt PDR001 until toxicity recovers to Grade ≤2 or baseline 
 Once recovered restart PDR001 treatment at the same dose and schedule 
AE resolution to ≤ Grade 2 or baseline must occur within a maximum period of 12 weeks since Grade 3 or 4 event has been identified, otherwise PDR001 must be permanently discontinued
 
3rd occurrence: Permanently discontinue PDR001.

Febrile Neutropenia	Apply Institutional guidelines	Follow- neutropenia Grade 4 requirements (above)
Thrombocytopenia (NCI-CTCAE v4.03)		
Grade 1, 2, 3 without clinical significant bleeding	Grade 3: monitoring blood test more frequently (every 7 days)	Continue PDR001 treatment

Hematologic suspected AEs (NCI-CTCAE v4.03)		
Grade	Recommended Adverse Event management guidelines	Mandatory Dose Modification requirements
Grade 3 with clinical significant bleeding OR Grade 4	Grade 3: monitoring blood test more frequently (every 3-5 days)	
1st occurrence:
 
 ● Interrupt PDR001 until toxicity resolves to Grade ≤ 2 or baseline. 
 ● Once recovered restart PDR001 treatment at the same dose and schedule 
2nd occurrence:
 
 ● Interrupt PDR001 until toxicity resolves to Grade ≤ 2 or baseline 
 ● Once recovered restart PDR001 treatment at the same dose and schedule 
AE resolution to \leq Grade 2 or baseline must occur within a maximum period of 12 weeks since Grade 3 with clinically significant bleeding or Grade 4 event has been identified, otherwise PDR001 must be permanently discontinued.
 
3rd occurrence: Permanently discontinue PDR001.

Table 6-12 Mandatory dose modification requirements and recommended clinical management guidelines for non-hematologic adverse events suspected related to study treatment

Non-Hematologic suspected AEs (except Grade 2 alopecia, Grade 2 fatigue) (NCI-CTCAE v4.03)		
Grade	Recommended Adverse Event management guidelines	Mandatory Dose Modification requirements
Grade 1-2 tolerable	
 ● Monitor closely ● Provide supportive care according to institutional standards 	Continue PDR001 treatment at the same dose and schedule
Grade 2 intolerable or Grade 3	
 ● Monitor closely ● Provide supportive care according to institutional standards 	
1st or 2nd occurrence:
 
 ● Interrupt PDR001 until toxicity recovers to Grade ≤ 1 or baseline. 
 ● Once recovered restart PDR001 treatment at the same dose and schedule 
AE resolution to Grade ≤ 1 or baseline must occur within a maximum period of 12 weeks since intolerable Grade 2 or Grade 3 event has been identified, otherwise PDR001 must be permanently discontinued.
 
3rd occurrence: Permanently discontinue PDR001

Grade 4	
 ● Monitor closely ● Provide supportive care according to institutional standards 	
1st occurrence:
 
 ● Interrupt PDR001 
 ● Consider permanently discontinuing PDR001. If benefit risk assessment support treatment continuation, restart PDR001 treatment at the same dose and schedule. 
2nd occurrence: Permanently discontinue PDR001

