Other study treatment	Any drug administered to the patient as part of the required study procedures that was not included in the investigational treatment
Personal Data	Patient information collected by the Investigator that is transferred to Novartis for the purpose of the clinical trial. This data includes patient identifier information, study information and biological samples.
Subject Number (Subject No.)	A unique identifying number assigned to each patient who enrolls in the study
Period	A subdivision of the study timeline; divides stages into smaller functional segments such as screening, baseline, titration, washout, etc.
Stage in cancer	The extent of a cancer in the body. Staging is usually based on the size of the tumor, whether lymph nodes contain cancer, and whether the cancer has spread from the original site to other parts of the body
Stop study participation	Point/time at which the patient came in for a final evaluation visit or when study treatment was discontinued whichever is later
Study treatment	Includes any drug or combination of drugs in any study arm administered to the patient as part of the required study procedures, including placebo and active drug run-ins. In specific examples, it is important to judge investigational treatment component relationship relative to a study treatment combination; study treatment in this case refers to the investigational and non-investigational treatments in combination.
Study treatment interruption	Includes any delay or withholding of study treatment for any reason as well as an interruption during an infusion of study treatment for any reason
Study treatment discontinuation	Point/time when patient permanently stops taking study treatment for any reason
Variable	Identifier used in the data analysis; derived directly or indirectly from data collected using specified assessments at specified timepoints
Withdrawal of consent	Withdrawal of consent from the study occurs only when a patient does not want to participate in the study any longer, and does not allow any further collection of personal data

Amendment 3 (24-May-2018)

Amendment rationale

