6.3.1.1 Dose modification and dose interruption for PDR001

General dose modification instructions:

No changes in the dose of PDR001 are allowed.

AEs are to be graded according to NCI-CTCAE v4.03 (ctep.cancer.gov). All dose interruptions and the reasons for dose interruption must be documented in the eCRF.

Treatment of patients with AEs suspected to be related to PDR001 including those of potential immune-mediated etiology (irAE) (see definition in [Section 6.3.1.2.1](#)) must be permanently discontinued if the following occurs within 12 weeks:

- AEs do not recover to \leq grade 1 or baseline
- The dose of steroids (for the management of irAEs) is > 10 mg/day prednisone or equivalent (or as indicated in the tables below)

The 12 weeks' period starts from the time an irAE reaches a severity grade that requires PDR001 interruption.

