6.4.3 Prohibited concomitant therapy

During the course of the study, patients must not receive other additional investigational drugs, devices, chemotherapy, or any other therapies that may be active against cancer or modulate the immune responses. However, limited-field palliative radiotherapy may be allowed as concomitant therapy. Such local therapies administered during the study treatment must be entered into the CRF. Additionally, no other therapeutic monoclonal antibodies and no immunosuppressive medication may be administered while on this study unless given for the management of immune toxicity.

The use of somatostatin analogs or any other medications administered to control active symptoms related to carcinoid syndrome is not permitted during the study unless there is a change to functional status (Section 6.4.4.1).

The use of systemic steroid therapy and other immunosuppressive drugs is not allowed except for the treatment of infusion reaction, irAEs, and for prophylaxis against imaging contrast dye allergy or replacement-dose steroids in the setting of adrenal insufficiency (providing this is < 10 mg/day prednisone or equivalent), or transient exacerbations of other underlying diseases such as COPD requiring treatment for \leq 3 weeks. If systemic corticosteroids are required for the control of infusion reactions or irAEs, it must be tapered and be at non-immunosuppressive doses (< 10 mg/day of prednisone or equivalent) before the next administration of study treatment. If the dose of prednisone or equivalent cannot be reduced to less than 10 mg/day before the administration of next dose of study treatment then PDR001 must be discontinued.

The use of live vaccines is not allowed through the whole duration of the study. Inactivated vaccines are allowed.

There are no prohibited therapies during the post-treatment follow-up period.

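### Three protocol sections conflict on whether PDR001 may be given at exactly 10 mg/day prednisone, and the time limit in one of them is ambiguous

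*Protocol*

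**What the plan says.** Section 6.3.1.2.2 (taper guidance): "Once corticosteroid tapering is achieved at a level of 10 mg of prednisone/day (or equivalent), treatment with PDR001 can be restarted", with a pointer to the dose-modification tables.

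Section 6.3.1.1 (general dose modification): treatment "must be permanently discontinued if the following occurs within 12 weeks", and one of the two listed conditions is: "The dose of steroids (for the management of irAEs) is > 10 mg/day prednisone or equivalent (or as indicated in the tables below". The clock is defined: "The 12 weeks' period starts from the time an irAE reaches a severity grade that requires PDR001 interruption".

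Section 6.4.3 (prohibited therapy), on steroids given for infusion reactions or immune-related events: "it must be tapered and be at non-immunosuppressive doses (< 10 mg/day of prednisone or equivalent) before the next administration of study treatment". It goes on to say that when steroids "cannot be reduced to less than 10 mg/day before the administration of next dose of study treatment then PDR001 must be discontinued". The glossary defines study treatment discontinuation as "Point/time when patient permanently stops taking study treatment for any reason".

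Section 6.1.1 sets dosing every 4 weeks with a window of 7 days either side, and allows interruption for up to 12 weeks.

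**The concern.** The three sections treat the same dose differently. A patient tapered to exactly 10 mg/day may restart under one section and may not be dosed under another. If that patient cannot go lower, one section ends treatment for good while the other two allow it to continue. The protocol makes dose-modification requirements mandatory (Section 6.3.1.2.1) and permits no authorised deviations (Section 12), so an investigator who follows one rule can breach another.

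The outcomes feed planned summaries: interruptions and permanent discontinuations with reasons (SAP 2.4.1), adverse events of special interest that lead to discontinuation or need immunosuppressive medication (SAP 2.8.1.1), and protocol deviations (SAP 2.3.1). Inconsistent application would blur all three, apart from the safety question itself.

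**Working it through.** The plan states no figure on this point, so there is nothing to reproduce.

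**Step 1: the dose limit.** The sections at exactly 10 mg/day:

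| Section | Condition | At exactly 10 mg/day |
|---|---|---|
| 6.3.1.2.2 | restart once at 10 mg/day | restart allowed |
| 6.3.1.1 | stop if above 10 mg/day | stop not triggered |
| 6.4.3 | below 10 mg/day before the next administration | dosing not allowed; discontinue if it cannot be lowered before the next dose |

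Sections 6.3.1.1 and 6.3.1.2.2 both refer to the tables. The mandatory columns of Tables 6-2 to 6-10 give no steroid limit in mg/day. The nearest is Table 6-2, which asks for appropriate tapering before restart after Grade 3 diarrhea/colitis. The conflict follows from the text and needs no assumption.

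**Step 2: the time limit.** Section 6.4.3 gives no number of days. If the next dose is the next scheduled one, at most 28 days are available, or 28 + 7 = 35 with the window, and fewer if the event starts mid-cycle. Section 6.3.1.1 gives 12 × 7 = 84 days, taking its wording to mean that steroids are still above 10 mg/day when the 12 weeks end. If the next dose may be delayed, the two can coexist.

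**Step 3: what the guidance taper implies under the scheduled reading.**

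Inputs: decrements of 2.5 to 5 mg every 3 to 7 days (Section 6.3.1.2.2); starting doses of 0.5 to 1 mg/kg and 1 to 2 mg/kg (for example Table 6-5, Grades 2 and 3). Assumption: body weight 70 kg. Time on full dose before the taper is ignored, which favours meeting every limit.

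Steps to 10 mg = (weight × mg/kg − 10) ÷ decrement. Getting below 10 mg takes one more step in these cases. Days = steps × days per step.

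From 1 mg/kg (70 mg), fastest pace: (70 − 10) ÷ 5 = 12 steps, 12 × 3 = 36 days to 10 mg and 13 × 3 = 39 days to below 10 mg. Slowest pace: 60 ÷ 2.5 = 24 steps, 24 × 7 = 168 days and 25 × 7 = 175 days.

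Days to 10 mg / days to below 10 mg, at 70 kg:

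| Start | 5 mg per 3 d | 2.5 mg per 3 d | 5 mg per 7 d | 2.5 mg per 7 d |
|---|---|---|---|---|
| 0.5 mg/kg (35 mg) | 15 / 18 | 30 / 33 | 35 / 42 | 70 / 77 |
| 1 mg/kg (70 mg) | 36 / 39 | 72 / 75 | 84 / 91 | 168 / 175 |
| 2 mg/kg (140 mg) | 78 / 81 | 156 / 159 | 182 / 189 | 364 / 371 |

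For Section 6.4.3, compare the second figure in each cell with 28 or 35 days. From 0.5 mg/kg, one of four paces meets 28 days and two meet 35. From 1 or 2 mg/kg, none does at this weight. For Section 6.3.1.1, compare the first figure with 84 days. The sections diverge only where 35 days are missed and 84 are met, such as 36 / 39 or 70 / 77. At 168 / 175 both sections would stop treatment.

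**Step 4: the same result without a body weight.** To be below 10 mg/day within T days, the starting dose must be less than 10 + (whole steps in T) × decrement:

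- 28 days: less than 10 + 9 × 5 = 55 mg (fastest), or 10 + 4 × 2.5 = 20 mg (slowest).
- 35 days: less than 10 + 11 × 5 = 65 mg, or 10 + 5 × 2.5 = 22.5 mg.
- 84 days: less than 10 + 28 × 5 = 150 mg, or 10 + 12 × 2.5 = 40 mg.

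The stated taper lengths point the same way: at least 4 weeks in Section 6.3.1.2.2, and 6 to 8 weeks or 45 to 60 days for certain Grade 3 colitis cases in Table 6-2, where restart is foreseen after a first occurrence.

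**The case against.** Four points can be made against this.

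First, Section 6.4.3 does not order discontinuation merely because a patient is at 10 mg/day on a given day. It does so only if the dose cannot be brought lower before the next dose. For a patient still tapering, the mismatch usually amounts to one more step of 3 to 7 days, which fits the dosing window. This stands: the large consequence falls on patients who cannot go below 10 mg/day. It does not remove the conflict over whether dosing at 10 mg/day is allowed.

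Second, a reader might infer that the time limits flatly contradict each other. The documents do not support that. Section 6.4.3 does not specify the scheduled dose, whereas Table 6-9 does when it means it. Section 6.3.1 defines interruption to include delay, and Sections 6.1.1 and 6.3.1.1 allow 12 weeks. Section 6.4.3 can therefore be read as a condition on a delayed dose. It is an ambiguity, though one that no passage resolves.

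Third, a reader might infer that the protocol's taper usually fails the shorter limit, or that most patients would be stopped. There are no patient frequencies to support this. Some permitted tapers meet 28 days, the pace is guidance that sites may adapt to local practice (Section 6.3.1.2.1), and the longest tapers also miss the 12 weeks.

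Fourth, the reach is limited. Recruitment closed on 20-Sep-2017, so a clarification now affects only patients still on treatment, and the ORR calculation does not use these rules. Both are right. Patients may, however, continue after the 10-Aug-2018 cut-off (Section 4.1), so the rules stay in force for them.

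**Conclusion.** The conflict over the dose limit is established from the text alone: at exactly 10 mg/day, Sections 6.3.1.1 and 6.3.1.2.2 allow PDR001 and Section 6.4.3 does not. The time limit in Section 6.4.3 is ambiguous, not shown to be contradictory.

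The size of the timing problem depends on reading the next dose as the scheduled one, on the 70 kg assumption, on the starting dose, and on sites following the guidance pace. On those terms, many but not all permitted tapers would miss the shorter limit. Nothing here estimates how many patients were or would be affected. The point bears on safety conduct and on the exposure, discontinuation and deviation summaries, not on the primary endpoint.

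**What to change.** Reconcile Sections 6.3.1.1, 6.3.1.2.2 and 6.4.3, and the dose-modification tables to which the first two refer, so that:

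- one steroid threshold applies, with its boundary stated (whether exactly 10 mg/day counts as acceptable);
- one time limit applies, with its starting point;
- the next dose is defined as either the scheduled or the delayed dose.

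The values are for the sponsor's clinical team; this review takes no view on them.

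The text change is small, but it needs a written amendment with sponsor and ethics approval, and health authority approval where required (Section 12.1). It needs no new data collection and no change to the analysis. When reporting discontinuations and deviations, it would help to state which reading sites applied.

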6.3.2 Dose adjustments for QTcF prolongation

Not applicable

6.3.3 Follow-up for toxicities

Serologic, histologic (tumor sample) and immunological assessments should be performed as deemed appropriate by the Investigator to verify the immune-related nature of the AE and to exclude alternative explanations. Recommendations ([Section 6.3](#)) have been developed to assist investigators in assessing and managing the most frequently occurring irAEs.

Patients whose treatment is interrupted or permanently discontinued due to an irAE, AE or clinically significant laboratory value, must be followed-up at least once a week (or more frequently if required by institutional practices, or if clinically indicated) for 30 days, and subsequently at approximately 30-day intervals (or more frequently if required by institutional practices, or if clinically indicated), until resolution or stabilization of the event, whichever comes first. Appropriate clinical experts should be consulted as deemed necessary.

If an AE is suspected to be immune-related, the relevant immunological assessments (e.g. rheumatoid factor, anti-DNA Ab, etc.) should be performed. If cytokine release syndrome is suspected, the assessments outlined in [Section 7.2.6.6.5](#) must be performed.

All patients must be followed-up for AEs and SAEs for 150 days following the last dose of PDR001. However, if the patient begins post-treatment antineoplastic medication during the period between the 30-Day safety follow-up and 150-Day safety follow-up, the collection of new SAEs and AEs unrelated to study medication will stop, and thereafter only suspected SAEs and suspected AEs will continue to be collected to Day 150. If SAEs suspected to be related to study medication occur beyond Day 150, information should also be collected. [Section 6.3.3.1](#) outline the follow-up evaluations recommended for selected toxicities.

6.3.3.1 Follow up on potential drug-induced liver injury (DILI) cases

Patients with transaminase increase combined with TBIL increase may be indicative of potential DILI, and should be considered as clinically important events.

The threshold for potential DILI may depend on the patient's baseline AST/ALT and TBIL value; patients meeting any of the following criteria will require further follow-up as outlined below:

- For patients with normal ALT and AST and TBIL value at baseline: AST or ALT > 3.0 x ULN combined with TBIL > 2.0 x ULN
- For patients with elevated AST or ALT or TBIL value at baseline: [AST or ALT > 2 x baseline AND > 3.0 x ULN] OR [AST or ALT > 8.0 x ULN], combined with [TBIL > 2 x baseline AND > 2.0 x ULN]

Medical review needs to ensure that liver test elevations are not caused by cholestasis, defined as ALP elevation > 2.0 x ULN with R value < 2 in patients without bone metastasis, or elevation of ALP liver fraction in patients with bone metastasis.

Note: (The R value is calculated by dividing the ALT by the ALP, using multiples of the ULN for both values. It denotes whether the relative pattern of ALT and/or ALP elevation is due to cholestatic ($R \leq 2$), hepatocellular ($R \geq 5$), or mixed ($R > 2$ and < 5) liver injury).

In the absence of cholestasis, these patients should be immediately discontinued from study drug treatment, and repeat LFT testing as soon as possible, preferably within 48 hours from the awareness of the abnormal results. The evaluation should include laboratory tests, detailed history, physical assessment and the possibility of liver metastasis or new liver lesions, obstructions/compressions, etc.

1. Laboratory tests should include ALT, AST, albumin, creatine kinase, total bilirubin, direct and indirect bilirubin, GGT, prothrombin time (PT)/INR and alkaline phosphatase.
2. A detailed history, including relevant information, such as review of ethanol, concomitant medications, herbal remedies, supplement consumption, history of any pre-existing liver conditions or risk factors, should be collected.
3. Further testing for acute hepatitis A, B, C or E infection and liver imaging (e.g. biliary tract) may be warranted.
4. Obtain PK sample, as close as possible to last dose of study drug, if PK analysis is performed in the study.
5. Additional testing for other hepatotropic viral infection (CMV, EBV or HSV), autoimmune hepatitis or liver biopsy may be considered as clinically indicated or after consultation with specialist/hepatologist.

All cases confirmed on repeat testing meeting the laboratory criteria defined above, with no other alternative cause for LFT abnormalities identified should be considered as “medically significant”, thus, met the definition of SAE ([Section 8.2.1](#)) and reported as SAE using the term “potential drug-induced liver injury”. All events should be followed up with the outcome clearly documented.

6.4 Concomitant medications

6.4.1 Permitted concomitant therapy

In general, concomitant medications and therapies deemed necessary for the supportive care (e.g. such as anti-emetics, anti-diarrhea) and safety of the patient are allowed except those prohibited in [Section 6.4.3](#). The following list includes permitted concomitant therapies:

- Medications to prevent or treat nausea or vomiting.
- Anti-diarrheal medications (e.g., loperamide) for patients who develop diarrhea.
- Pain medication to allow the patient to be as comfortable as possible.
- Localized radiotherapy and treatment with bisphosphonates for pre-existing, painful bone/liver metastases is permitted. The radiotherapy must be listed on the CRF.
- Immunosuppressive agents to treat suspected irAEs.
- Nutritional support or appetite stimulants (e.g. megestrol).
- Oxygen therapy and blood products or transfusions.
- Limited-field palliative radiotherapy may be allowed as concomitant therapy. Such local therapies administered during the study treatment must be listed on the CRF.

- Inactivated vaccines.
- The patient must be told to notify the investigational site about any new medications he/she takes after the start of the study drug. All medications (other than study drug) and significant non-drug therapies (including physical therapy, herbal/natural medications and blood transfusions) administered during the study must be listed on the Concomitant Medications.

